6.2.5 Final Visit (Month 14)

During the final visit medical history will be checked with the recording of any anomalies. Concomitant medication is also to be registered, together with any adverse event detected since the last visit or since the last plasma exchange session.

Plasma samples will be collected from the subjects (control and treatment group) to allow the pertinent tests. Additional plasma samples will be collected each time for storage at -70°C and possible future assays.

The following parameters will also be evaluated: biomarkers of AD (A β -40, A β -42, β -secretase, γ -secretase, cholesterol, LDL, HDL, VLDL, C-reactive protein, rheumatoid factor, IL-1b, IL-6, ferritin, TNF- α), coagulation factors (prothrombin time (Quick), aPTT, calcium and fibrinogen), proteinogram (total proteins, albumin, α_1 -globulina, α_2 -globulina, β -globulina, γ -globulina and IgG), other liver or kidney biochemical markers (AST, ALT, bilirubin, LDH and creatinine), troponin and serology (anti-HIV and HCV antibodies, and HBsAg antigen). In addition, a blood cell count will be performed, including: hematocrit, hemoglobin and erythrocytes, platelets and leukocytes (if an abnormal leukocyte count is recorded, it will be obligate to specify neutrophils, basophils, eosinophils, lymphocytes and monocytes).

During the final visit a MRI and a FDG-PET will also be performed.

The following tests will be performed to measure cognition, functionality, behavior, global evolution, impression and depression: ADAS-Cog, MMSE, NPS battery, ADCS-ADL, NPI, CDR-Sb, ADCS-CGIC, CSDD, CSSRS, QoL-AD and RUD-Lite[®] which are to be administered as indicated in the corresponding section. Likewise, anxiety and restlessness tests will be made based on the Overt Aggression Scale (OAS) and the Agitated Behavior Scale (ABS), whenever considered opportune.

Furthermore, it is obligatory to perform lumbar puncture, to collect CSF samples and assess the levels of A β -40, A β -42, P-tau, T-tau, β -secretase, γ -secretase, cholesterol, LDL, HDL, VLDL, C-reactive protein, IL-1b, IL-6, ferritin, TNF- α) and to perform standard CSF tests (cell counts, glucose, proteins and albumin).

These evaluations are considered to be the final data.

Control group

The control group will undergo the same schedule of assessments.

In case the final visit is conducted before completing the study, some assessments could be avoided. It will be decided case by case and depending on when the last assessments have been done.

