4.3 Planned Number of Subjects

A sample size of 312 subjects (78 per each of the 4 groups) will make it possible to detect with nearly 92% power for the first of the co-primary efficacy variable (the changes from baseline of the ADAS -Cog scores) a difference in the mean of 3 points between any of the treatment groups and the control group, assuming the common standard deviation (SD) to be 5.55 (according to the data obtained in the phase II study⁶⁵), with a level of significance of 5%. This same sample size provides over 98% power for second of the co-primary endpoint variables (the changes from baseline of the ADCS-ADL inventory scores) a difference in the mean of 6.69 points between any of the treatment groups and the control group, assuming the common standard deviation (SD) to be 10.0 (according to the data obtained in the phase II study), with a level of significance of 5%.

The study will have joint power for these co-primary endpoints of at least 90% ($0.92 \times 0.98 = 0.90$). The calculation makes the conservative assumption that these endpoints are independent. Since these endpoints may be positively correlated 90% should serve as a lower bound on power.

Assuming a global dropout rate of approximately 15%, the study would have to enroll 364 subjects to obtain 312 subjects for evaluation.

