4.4 Withdrawal Criteria and Planned Analyses of Withdrawals and Dropouts

The subject will be withdrawn from the study if:

- Prior to the first plasma exchange session, no plasma sample has been collected for possible future assays.
- Any serious adverse event is recorded, advising removal of the subject.
- The subject or his/her legal representative wishes to abandon the study and continue follow-up and normal treatment in the center.
- The investigator is of the opinion that treatment continuation is contraindicated.
- The subject fails to adhere to the study protocol.

The reason for withdrawal of the subject will be documented, and a final visit will be scheduled to obtain blood samples and to complete the pertinent tests. Whenever possible, these tests will be made on the same day as the final visit. No subject can be re-enrolled into the study after having been withdrawn from the study.

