The analysis of ADAS-Cog change from baseline to month 14, and the ADCS-ADL change from baseline to month 14, will also be analyzed using analysis of covariance (ANCOVA) with treatment group as a fixed effect, and the corresponding baseline value, age and AD severity as a covariate. A similar model will be calculated also for all other point in time where the end points are assessed. This is considered a sensitivity analysis, and comparison of the results to the MMRM results allows for a qualitative assessment of the impact of missing data.

The two co-primary efficacy end points, change from baseline in the ADAS-Cog score and the change from baseline in the ADCS-ADL inventory score will also be analyzed by a random slope model. For this random slope model, time will be used as continuous variable and all observations (scheduled and unscheduled) will be used with the actual study day, rather than the slotted point in time. Subject and time will be used as random factor using an unstructured covariance matrix. Fixed effects in this model are the baseline value, age, AD severity, time, treatment and treatment*time interaction. The treatment effect will be analyzed by evaluating the treatment * time interaction term. This is considered as a second sensitivity analysis.

This random slope model can be implemented in SAS by a code similar to the following:

```

proc mixed data=data;
class subj;
model change = baseline age AD severity time trt time*trt/ s;
random intercept time / type=un subject=subj;
repeated / type=vc subject=subj;
run;

```

Possible drop-outs during the treatment phase will not only reduce the available sample size for the final analysis, drop-outs might not be at random and can, therefore, introduce bias to the analysis. Patients who experience less benefit from the treatment might have a higher probability to discontinue the treatment compared to patients who have a better outcome. Therefore, the possible impact of the drop-outs needs be evaluated. The baseline values and the changes from baseline in the ADAS-Cog score and the ADCS-ADL inventory score to the intermediate visit, month 6, month 9, and month 12 will be compared descriptively for each treatment group between the patients who completed the study and patients who prematurely dropped out (Patients who did not complete the final assessment at month 14). Possible differences in the response to the treatment and the

	Title: Statistical Analysis Plan
	Project #: IG1002 AMBAR

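### Protocol 6.2.5 does not protect ADAS-Cog and ADCS-ADL from being waived at an early final visit, and it sets no interval and names no decision-maker

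*Protocol*

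**What the plan says.** Protocol 6.2.5 puts both co-primaries on the final-visit list: "The following tests will be performed to measure cognition, functionality, behavior, global evolution, impression and depression: ADAS-Cog, MMSE, NPS battery, ADCS-ADL". It closes with an exception for early leavers: "In case the final visit is conducted before completing the study, some assessments could be avoided. It will be decided case by case". The second sentence reads in full: "It will be decided case by case and depending on when the last assessments have been done". No test is protected, how recent is recent enough is not stated, and nobody is named to decide.

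Protocol 4.4 covers the same visit. After withdrawal, "a final visit will be scheduled to obtain blood samples and to complete the pertinent tests". Which tests are pertinent is not defined, and no later retrieval visit is described.

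Protocol 3.4 lists patients, caregivers and raters as blinded; other site staff are not listed. SAP 7 assigns each efficacy score to a visit window by study day and keeps the one nearest the target day. SAP 9.1.1 fits the primary MMRM to these slotted scores. Its random slope sensitivity model uses every observation on its actual day.

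**The concern.** An MMRM gives unbiased month-14 comparisons when drop-out depends only on scores that were recorded. The score at leaving is what makes that assumption credible. If a patient worsens, leaves and is not tested, the drop-out depends on something the model never sees. Those who worsened are then predicted too favourably, and the arm that loses more of them looks better.

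The SAP doubts the assumption itself: "Patients who experience less benefit from the treatment might have a higher probability to discontinue the treatment". Unequal drop-out is also plausible from the protocol's own rules. Appendices 11 and 12 withdraw a patient whose central catheter is removed for infection or who has a thromboembolic complication, and sham patients have no catheter in a vein. Such exits need not be driven by the score, but they belong to the weekly exchange period, so many could precede the first post-baseline test.

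**Working it through.** **The plan's own figures (Protocol 4.3).** With 78 per group and two-sided alpha 0.05:
- ADAS-Cog: SE = 5.55 × √(2/78) = 0.889; power = Φ(3/0.889 − 1.96) = 0.92.
- ADCS-ADL: SE = 10 × √(2/78) = 1.60; power = Φ(6.69/1.60 − 1.96) = 0.99.
- Joint: 0.922 × 0.987 = 0.91.

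These agree with the stated nearly 92%, over 98% and at least 90%. On enrolment the protocol says: "Assuming a global dropout rate of approximately 15%, the study would have to enroll 364 subjects to obtain 312 subjects for evaluation". 312/0.85 = 367, or 368 for four equal groups. The 364 corresponds to (364 − 312)/364 = 14.3%, close enough to about 15%.

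**Patients concerned.** 364 × 0.15 = 54.6, or 364 − 312 = 52. This is planned drop-out, not lost scores.

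**Which exit scores the MMRM would use.** Inputs are the windows and target days in the SAP 7 efficacy table. (The example in the text above that table gives a different month-6 range; the table is used here.) Assume scheduled tests fall on target days. An exit before the target day finds its window empty, so its score would be used. An exit after the target day finds a score already there, and the exit score is dropped.

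| Window (days) | Target | Empty days | Days since last post-baseline test |
|---|---|---|---|
| Intermediate, 2–93 | 45 | 2–44: 43 of 92 | none exists |
| Month 6, 94–184 | 141 | 94–140: 47 of 91 | 49–95 |
| Month 9, 185–268 | 225 | 185–224: 40 of 84 | 44–83 |
| Month 12, 269–343 | 309 | 269–308: 40 of 75 | 44–83 |
| Final, 344 onward | 375 | 344–374: 31 of 31 | 35–65 |

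- In filled windows the exit comes 1 to 48 days after a score that the MMRM already holds.
- In empty windows after a post-baseline test, the gap is 35 to 95 days. Exits on days 344–374 slot to month 14 itself, the primary time point.
- Before day 45, skipping the tests leaves no post-baseline score.

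**Ceiling on lost usable scores.** Assume exits uniform over time and every exit test skipped.
- Days 2–374: 201/373 = 54%; 0.15 × 0.54 = 8.1%; 364 × 0.081 = 29 patients.
- Days 2–343: 170/342 = 50%; 0.15 × 0.50 = 7.5%; 364 × 0.075 = 27 patients.

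**Bias.** The documents give no drop-out by arm, so this part rests on assumptions.
- No true ADAS-Cog effect; mean change 0.45 points per month.
- Random intercept SD 2, random slope SD 0.38 per month, error SD 2.5, at the five post-baseline visits. The implied month-14 SD is √(4 + 0.38² × 14² + 6.25) = 6.2, a little above the planned 5.55.
- Drop-out depends on the score at leaving, with log-odds 0.5 or 1.0 per SD, and is 20% v 10% or 18% v 6%.
- 60,000 patients per arm; unstructured multivariate normal fitted by EM.

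With the exit test done, the month-14 bias was within 0.04 points of zero. With every exit test skipped, two separately programmed runs gave 0.08–0.24 and 0.12–0.28 points in favour of the arm with more drop-out. Against the planned 3 points that is 0.08/3 = 3% to 0.28/3 = 9%. Against the SE of 0.889 it is 0.09 to 0.31 of a standard error.

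**The case against.** The strongest reply is that the clause carries its own limit. Skipping depends on when the tests were last done, so a reader who infers open-ended discretion has stopped before the end of the sentence. Applied sensibly, the rule costs the primary analysis nothing once a patient has a post-baseline score: with tests on target days, waiving only those done within the previous 34 days removes no score that the MMRM would use. This stands. It does not close the gap, because the protocol gives no number, and before day 45 the last assessment is baseline.

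Three stronger readings are tempting, and the documents do not support them.
- That about 15% of patients lose their last score. The 15% is planned drop-out, and the ceiling for the primary MMRM is about half of it.
- That the waiver is an arm-aware decision. Some site staff can know the arm: the sham manual has treated and sham patients scheduled apart, and the SAE form asks for the arm. But 6.2.5 names nobody, and the raters are blinded. All that can be said is that the decision is not necessarily blinded. The bias figures come from unequal drop-out, not from waivers that differ by arm.
- That 4.4 contradicts 6.2.5. Section 4.4 promises only tests judged pertinent, and recency is one way to judge that. The sections are compatible, but neither protects the co-primaries.

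The SAP also plans observed-case and LOCF ANCOVA, the random slope model, and a comparison of completers with drop-outs. These help to show the impact of missing data. None recovers a test that was not done.

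**Conclusion.** The gap is real and small. As written, either co-primary may be waived at the only visit planned after withdrawal, with no interval and a decision-maker who is unnamed and not necessarily blinded. A waiver soon after a scheduled test is harmless to the primary MMRM. A waiver after a longer gap, or before day 45, removes a score that it would use.

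The 27 to 29 patients are a ceiling that rests on on-target visits, uniform exit times and every exit test skipped. The bias of roughly 0.1 to 0.3 points further assumes unequal, score-driven drop-out, and in that model every skipped score lies a full visit interval after the previous one, which is the case the recency clause argues against. Low severity: a cheap improvement, not a threat to the trial's conclusion.

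**What to change.** In Protocol 6.2.5, state that ADAS-Cog and ADCS-ADL are always done at an early final visit unless the same test was done, after baseline, within a fixed short interval. Limit the case-by-case waiver to other assessments, such as imaging, lumbar puncture and serology. In 4.4, refer to this rule in place of the undefined set of tests.

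Four weeks would serve as the interval. It is shorter than the smallest gap that leads to an empty window after a post-baseline test (35 days, or 30 if the scheduled visit was 5 days late). The documents give no source for 4 weeks; any fixed value below 30 days would do the same. The interval should run from a post-baseline test only, since a baseline test could otherwise excuse an exit in the first weeks.

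The cost is a sentence or two of protocol text and one extra test session for some leaving patients. Some of those scores will fall in filled windows and be used only by the random slope model.

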6.2.6 Description of the Response Evaluation Methods

Medical history will be performed according to usual practice. Physical examination likewise will be performed according to the practice of the investigator. The investigator will carry out a general evaluation of the body systems, together with a full physical examination during the initial visit and again at the end of follow-up. The vital signs will be measured according to standard practice of the investigator.

Blood samples will be drawn according to standard practice of the center for the obtainment of blood, plasma and serum.

The amount of blood and CSF to be collected for all the tests will correspond to the amount needed for the assays in each visit or procedure. The precise amount of each sample will be established according to the requirements of the specific laboratory performing the analysis. As a recommendation, the minimum amounts are:

- Plasma samples for frozen back-up (-70°C): 10 mL of blood which, once processed, will be divided into three equal plasma aliquots in three cryopreservation tubes.
- From the plasma bag corresponding to each plasma exchange (FPE and LVPE), six samples will be obtained, with a maximum volume of two ml each, at each of the following time points: 30 minutes after starting replacement, after one hour, and at the end of the procedure. Thus, 18 plasma samples will also be obtained in each replacement session. The removed plasma bag from the FPE and LVPE will also be collected. These samples will be collected in some selected sites.
- A β and P-tau: 10 mL of blood (to obtain 5 mL of plasma) with EDTA (collection in polypropylene tubes is needed, since A β adheres to glass). In addition, 10 mL of blood with EDTAK2 will be obtained separately to assess A β in blood.
- Genetic markers: 4 mL of blood (approximately 2 mL of plasma) with EDTA.
- Coagulation parameters: 5 mL of blood (collected according to standard practice of the laboratory).
- Hematological tests: 5 mL of blood (collected according to standard practice of the laboratory).
- Proteinogram, biochemistry (kidney and liver function), and serology: 10 mL of blood (collected according to standard practice of the laboratory).
- CSF: At least a minimum of 5 mL and a maximum of 10 mL of CSF will be obtained according to the standard technique employed in the center. The sample will be divided into three aliquots: 3 mL for general tests (cell count, glucose, proteins and albumin), 3 mL for A β and P-tau (collected in polypropylene tubes), and 4 mL for frozen back-up (-70°C), stored in cryopreservation tubes.

The CSF aliquot destined for general testing should not be frozen but kept at room temperature, with immediate analysis. The other two aliquots can be immediately frozen, however, future testing cannot be done if >10 erythrocytes are detected. To avoid rejection of the sample, these aliquots may be centrifuged and the clarified CSF saved to eliminate any possible residual cells.

In the event of insufficient blood or plasma sample volume, priority should center on the measurements of A β and P-tau, then reserving three mL for frozen back-up, and the rest for testing according to the course of the study and investigator criterion (e.g., during the Intensive treatment phase the coagulation parameters are a greater priority than the

proteinogram; in contrast, during screening or the final visit, serology is the most important aspect).

In the event of insufficient CSF volume, priority is to center on the A β and P-tau measurements, then reserving two mL for frozen back-up, and the rest for general testing (particularly cell counts).

During the visits, and after blood collection, processing of the samples to obtain the plasma and/or serum is to be made within two hours. The blood and plasma and/or serum samples will be collected and taken immediately to the site laboratory for processing.

The serum and/or plasma samples can be analyzed on the same day (depending on the standard practice of the laboratory and test involved), or stored at -20°C for analysis within no more than two months after collection.

The routine hematological tests are to be made within a maximum of 12 hours after blood or CSF collection. Prior to analysis, the samples can be kept at 2-8°C, with the exception of the CSF samples, which must be kept at room temperature.

The plasma and CSF samples collected for possible future assays will be stored at -70°C.

Hematological, coagulation, and kidney and liver function tests will be performed by the standard practices of the laboratory.

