Albutein[®] 5% will be used according to the instructions of the **Full Prescribing Information (Appendix 1)**. The solution is normally clear to slightly opalescent. Do not use the product if the solution is cloudy or has precipitated. The product must be at body temperature before use. Do not dilute with water for injections. Once the container is open, the contents must be administered immediately. Unused contents must be discarded. No remaining product in an opened container can be stored in the refrigerator and used at a later time.

The vital signs of each subject (blood pressure, heart rate, respiratory rate, and body temperature) are to be monitored 15-30 minutes before replacement, during and again 15-30 minutes after the procedure, and as often as considered opportune by the investigator. The coagulation parameters must also be controlled, particularly fibrinogen concentration. In the case of any relevant alteration in the coagulation parameters, replacement must be suspended and no further sessions will be carried out until the parameters return to adequate levels (see sections 5.2.1 and 5.2.2).

Low-volume plasma exchanges (Maintenance treatment period)

In all sites where the low-volume replacement session will be performed, a device based on regular plasma donation (Auto-C, Fenwal, Illinois, USA with FDA PMA approval # BP850001 or Aurora, Fenwal, Illinois, USA with FDA 510(k) clearance # BK110072) will be tested (see **Appendix 3** for device protocol). The Auto-C (FDA PMA approval # BP850001) or Aurora (FDA 510(k) clearance # BK110072) based devices are used with the objective of offering the patient a procedure that is similar to a conventional plasma donation with the difference that albumin or IVIG will be infused at the end of the plasmapheresis.

Low volume plasma exchange (LVPE) will be carried out through a peripheral line. The removed plasma volume will be similar to that of a plasma donation (690 to 880 mL) and will depend on patient's weight.

The control group will undergo simulated (sham) low volume plasma exchange which will last approximately the same time as the subjects in the treatment group.

Albumin

Albutein[®] 20% will be infused at the end of the corresponding plasmapheresis using Auto-C (FDA PMA approval # BP850001) or Aurora (FDA 510(k) clearance # BK110072) based devices. During the Maintenance period the dosing will be as follows:

- 1st arm: 200 mL (40 g, 9 plasmaphereses)

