5.2 Criteria for Treatment Modification or Interruption

5.2.1 Criteria for Modifying Regimens

In the case of any relevant alteration in the coagulation parameters, full plasma replacement (Intensive period) is to be suspended and no further sessions will be carried out until the parameters return to adequate levels.

Replacement is to be postponed 24 hours if fibrinogen <1 g/L or the prothrombin time (Quick) <60% of the control value.

Platelet depletion to below 100,000/ μ L is also an indication for replacement suspension.

Relevant alterations of coagulation parameters are not expected to occur with the low-volume plasma exchanges (Maintenance period).

If any adverse event occurs during the infusion of Flebogamma[®] DIF one of the following actions will be carried out taking into account the nature and severity of the event:

- To stop the infusion.
- To reduce progressively the infusion rate until the symptoms disappear.

After re-evaluation the adverse event, it can be proceed as follows:

- To restart the infusion or to increase as of a tolerated rate (once the symptoms have disappear) or
- To definitely stop the infusion.

If a patient presents an adverse event two times with the same infusion rate, the following doses will be administered at the maximum tolerated rate.

5.2.2 *Special Warnings and Precautions for Use*

Full plasma exchange is a safe technique that may induce very well-known and therefore preventable and controllable, adverse reactions, according to the guidelines provided below. In any case, and considering the special vulnerability of the patients studied, a number of precautions (in addition to the habitual measures) have been taken to minimize the risks of the procedure:

1. Plasma exchange will be carried out by specialized nursing personnel, under direct and continuous supervision by the specialists.
2. Subjects will be required to remain in the center before and after the procedure for longer periods of time than usual.
3. Vital signs and laboratory test parameters will be monitored more frequently than usual.
4. The treatment suspension / postponement criteria are clearly established.

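### When CSF or blood is short, Protocol 6.2.6 fills the frozen back-up before the CSF cell count and the coagulation and platelet tests; a 5 mL CSF sample with the stated 3 mL assay aliquot leaves nothing for the cell count

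*Protocol*

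**What the plan says.** **CSF.** Protocol 6.2.6 sets the volume: "At least a minimum of 5 mL and a maximum of 10 mL of CSF will be obtained". The planned split is 3 mL for general tests, which include the cell count, 3 mL for Aβ and P-tau, and "4 mL for frozen back-up (-70°C), stored in cryopreservation tubes". If CSF is short, Aβ and P-tau come first, "then reserving two mL for frozen back-up, and the rest for general testing (particularly cell counts"). Of the two aliquots that may be frozen at once, the section says "future testing cannot be done if >10 erythrocytes are detected". It allows them to be centrifuged to avoid rejection. Appendix 8 marks CSF cell counts as mandatory for all groups at screening, the intermediate visit and the final visit. CSF Aβ and tau are secondary efficacy variables (Protocol 6.1.2; SAP 7.1.11).

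**Blood.** The shortage rule again puts Aβ and P-tau first, "then reserving three mL for frozen back-up, and the rest for testing according to the course of the study and investigator criterion". An example adds that in the intensive phase coagulation ranks above the proteinogram. Section 5.1.3 states: "The coagulation parameters must also be controlled, particularly fibrinogen concentration", and requires suspension after a relevant coagulation change. Section 5.2.1 postpones an exchange by 24 hours for fibrinogen below 1 g/L or a Quick value below 60% of control. "Platelet depletion to below 100,000" per µL is listed there as a reason for suspension. Section 6.2.2 schedules the coagulation tests and the cell count with platelets before each full exchange, and again afterwards. Section 4.4 withdraws a subject for whom no plasma was stored before the first exchange.

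**The concern.** In both fluids, material stored for possible later use is served before tests that the protocol itself relies on.

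For CSF, the cell count comes out of the aliquot that is served last, but its erythrocyte result decides whether the other aliquots may be tested. A sample that meets the stated minimum could yield Aβ and tau values for a secondary endpoint with no count to show whether the rejection rule applied. The mandatory cell count would also be missing.

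For blood, the tests behind the postponement and suspension criteria are taken from whatever is left after the biomarker and back-up tubes. The preference for coagulation over the proteinogram works only inside that remainder. A site following 6.2.6 to the letter with a short draw could store plasma and still lack results that 5.1.3, 5.2.1 and 6.2.2 call for.

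**Working it through.** **1. The plan's own CSF figure.** The three aliquots sum to 3 + 3 + 4 = 10 mL, the stated maximum. The planned split therefore fits only a 10 mL sample.

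**2. CSF under the shortage rule.** Remainder for general tests = V - 3 (Aβ/P-tau, the stated aliquot) - 2 (back-up).

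| CSF collected (mL) | Left for general tests (mL) |
|---|---|
| 5 | 0 |
| 5.5 | 0.5 |
| 6 | 1 |
| 7 | 2 |
| 8 | 3 |

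The full 3 mL general aliquot is restored only at 8 mL.

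**3. Sensitivity to the assay volume.** The shortage sentence fixes the back-up at 2 mL but gives no reduced volume for Aβ/P-tau. If the assay used less than 3 mL (an assumption), a 5 mL sample would leave 5 - 2 - a for general tests:

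- a = 2.5 mL leaves 0.5 mL
- a = 2 mL leaves 1 mL
- a = 1.5 mL leaves 1.5 mL
- a = 1 mL leaves 2 mL

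**4. Blood served before coagulation and haematology.** The inputs are the volumes recommended in 6.2.6:

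- Aβ/P-tau: 10 mL of blood, giving 5 mL of plasma
- a separate EDTAK2 tube for Aβ in blood: 10 mL
- coagulation: 5 mL
- haematology, which includes platelets: 5 mL
- frozen back-up: 10 mL when blood is not short
- proteinogram, biochemistry and serology: 10 mL

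Without genetic markers the full list is 10 + 10 + 5 + 5 + 10 + 10 = 50 mL.

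The reserved 3 mL of back-up is 3 mL of blood, or 3 / 0.5 = 6 mL of blood if it means plasma at the protocol's own yield. The separate tube may or may not count as part of the first priority.

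| Aβ tubes (mL) | Back-up as blood (mL) | Served first (mL) | Plus 10 mL for coagulation and haematology |
|---|---|---|---|
| 10 | 3 | 13 | 23 |
| 10 | 6 | 16 | 26 |
| 20 | 3 | 23 | 33 |
| 20 | 6 | 26 | 36 |

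So 13 to 26 mL is served first, which is 26% to 52% of the 50 mL list. Both sets of tests are fully covered only from 23 to 36 mL.

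**5. P-tau in blood.** The blood shortage rule names P-tau. Protocol 6.1.2 and 7.3 and SAP 7.1.11 place P-tau in CSF only, and the plasma biomarker lists in 6.2.2 and Appendix 8 omit it. It shares the Aβ tube, so none of the volumes above depends on it.

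**The case against.** Several points on the other side stand.

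- The 6.2.6 volumes are a recommendation. The laboratory sets the exact amounts, and Appendix 9 refers to a laboratory manual that is not among the documents. The assay may need less than 3 mL, and the mention of cell counts in the CSF rule suggests that a remainder was expected. The 0 mL result is therefore conditional on the stated aliquot.
- Centrifugation deals with residual cells. It is optional, however, and it supplies no count for the rejection rule.
- Blood is drawn into separate tubes rather than from one pool. The 13 to 26 mL range shows what the written order implies; it does not predict what a site would collect.

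A reader might infer that 6.2.6 allows a full exchange without coagulation or platelet results, or that it contradicts the suspension criteria every time blood is short. The documents do not support either reading. Sections 5.1.3, 5.2.1 and 6.2.2 still require the tests, 6.2.6 waives none of them, and nothing forbids a further draw. What remains is a priority order that sits badly with those requirements and does not mention them.

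A reader might also infer the loss of a safety endpoint. CSF cell count is not among the safety variables in 6.1.3 or 8.3. What is at stake is the check on the sample and a test scheduled as mandatory.

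**Conclusion.** The CSF part is the firmer one. A 5 mL sample meets the protocol, yet with the stated 3 mL assay aliquot it leaves 0 mL for the cell count. The general aliquot stays short of its planned 3 mL until 8 mL is collected. With an assumed assay volume of 1 to 2.5 mL, the shortfall at 5 mL is partial, with 2 to 0.5 mL left. It does not follow that CSF Aβ or tau values will be contaminated, only that contamination could go unchecked in a minimum-volume sample.

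The blood part is an ordering that needs reconciling: 13 to 26 mL is ranked ahead of tests on which postponement and suspension depend. The width of that range comes from two things the text leaves open: whether the EDTAK2 tube counts, and whether the 3 mL is blood or plasma.

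Both parts matter only when a sample is short, and the documents give no frequency for that.

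**What to change.** **CSF.** In the 6.2.6 shortage rule, reserve a small cell-count aliquot before the frozen back-up, with its volume set by the laboratory. Keep the Aβ/P-tau aliquot, and let the back-up take what remains. As an illustration only, at 5 mL with 3 mL kept for the assay, a 0.5 mL count aliquot leaves 1.5 mL of back-up and a 1 mL aliquot leaves 1 mL.

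**Blood.** Reconcile the shortage rule with 5.1.3, 5.2.1 and 6.2.2, so that frozen back-up cannot displace the coagulation and platelet tests required around each full exchange. Exempt the plasma sample stored before the first exchange, because 4.4 withdraws a subject who has none; simply putting back-up last would collide with that. The postponement and suspension criteria themselves are not changed. State whether the 3 mL is blood or plasma and whether the EDTAK2 tube belongs to the first priority. Check whether P-tau belongs in the blood rule.

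**Cost.** One paragraph in 6.2.6 and a matching entry in the laboratory manual. The price is less frozen back-up when samples are short.
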